8.12. Number of Trial Subjects

Up to 45 nasal and nasal pillows mask users for OSA therapy will be recruited into this trial.

8.13. Follow up Plan

Patients will receive standard care from their health care provider throughout and following the study.

This is to document that compensation to subjects(s) for trial related injury will be available.

STATISTICAL CONSIDERATIONS

9.5. Description of the Statistical Design

Since the trial is regarding the performance and acceptability of the trial device in order to inform product development, no statistical design is required.

9.6. Sample Size

From the 'Guidance for Industry and Food and Drug Administration Staff – Applying Human Factors and Usability Engineering to Optimize Medical Device Design' document issued on 3 February 2016, a number of 30 users will be sufficient to find a minimum of 97% of problems and on average can find 99% of all problems¹³. Additionally from previous experiences, a number of 30 users was not quite achieved when taking into account drop outs and no shows hence the recruitment drive for up to 45 participants has been set. .

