6.1. Synopsis

This clinical investigation is designed to evaluate the performance (treatment efficacy and leak), comfort (subjective feedback), stability (subjective feedback, leak) as well as the participant's overall acceptance of the Nasal mask amongst OSA participants. An important factor in this investigation will be the testing of all four seal sizes (small, medium, large and wide) as well as other changes and improvements made to the design of the mask from the previous two clinical trials (Clinical trial 5 USA- CIA-195 & Clinical Trial 6 - NZ – CIA-205).

Up to 45 OSA participants who currently use a nasal or nasal pillows CPAP mask will be recruited by Clinical Trials of Florida from their database of patients. (Phone script for recruiting in Appendix A).

This study will involve a baseline visit (Visit 1) where the patient's prescribed PAP therapy treatment settings will be gathered. An F&P ICON+ device will be issued to the participant (if required) during this visit as well as gaining their informed consent for the F&P Nasal mask (CIA-211) and the Anthropometric 3D Scanning study (CIA-107). This will be followed by the participants being fitted with the F&P Nasal mask during visit 2 as well as being asked a few questions in the form of a structured questionnaire. Their initial impressions, comments and photographs will be captured via recorded audio and video (with their consent). Visit 2 will take place 7 ± 5 days after Visit 1. The [redacted]

patients will come in for a final visit to return the trial mask and documentation and provide their feedback in the form of verbal comments and a structured questionnaire. Photographs will be captured as well as audio and video recorded during this visit. Visit 3 will take place 14 ± 5 days after Visit 2.

The mask and CPAP (if from the research pool) will be returned to the Institution at the conclusion of the trial and the participant will return to their previous mask and mode of device treatment. The Institution will recruit all patients within two weeks of the beginning of the study.

[figure not shown]
[figure not shown]
This study will be conducted in accordance with ICH/GCP Guidelines. No deviation from the protocol will be implemented without the prior review and approval of the sponsor except where it may be necessary to eliminate an immediate hazard to a research participant. In such case, the deviation will be reported to the sponsor as soon as possible.

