8.10. Patient Procedure

The study coordinator will ask the subjects whether they're interested to take part in the trial. Only eligible participants, that provide written informed consent, will be enrolled into the investigation.

[figure not shown]
[figure not shown]
EVENTS	Visit One	Visit Two	Phone Call	Visit Three
Informed consent	X			
ICON+ Premo/Auto given and instructions for use (if applicable)	X			
Commence baseline data gathering	X			

Participant Questionnaire (see Appendix)		X		
Mask fitting with F&P Nasal mask		X		
Head Measurements		X		
Static Leak Measurement		X		
Issue Sleep Diary (Appendix F)		X		
Issue complete Nasal mask with UI		X		
Researcher Questionnaire (see Appendix B)		X		
Baseline PAP device data downloaded		X		
Commence in-home trial of the F&P Nasal mask		X		
Phone call				X
Return the F&P Nasal mask				X
Returned loaned ICON+ Premo/Auto given and instructions for use (if applicable)				X
Return Sleep Diary				X
Participant Questionnaire (see Appendix)				X
Researcher Questionnaire (see Appendix B)				X
PAP device data downloaded				X

With the following section, the days ($\pm N$) reflects: the date that will begin for that section (\pm the range within which the visit is acceptable).

Clinical Trials of Florida will be providing compensation to the participant of \$40.00USD for each completed visit (a total of \$120USD for 3 visits). This will be paid after the conclusion of each visit or the withdrawal of the participant from the trial during any of the visits.

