9.10. Selection Criteria

All participants who consent, and are fitted with a mask that they attempt to sleep on will be included in the analysis. Please see section 8.10 for information on participant flow throughout the trial.

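### The 30-user detection figure in section 9.6 gives no assurance for home-use problems confined to one seal size, since at most one of the four seals can have 30 wearers among 45 participants

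*Combined protocol and SAP*

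**What the plan says.** Section 9.6 is the only sample-size rationale in the readable text. Citing human-factors guidance, it says that "a number of 30 users will be sufficient to find a minimum of 97% of problems" and "on average can find 99% of all problems". Neither statement is limited to a type of problem or to a part of the mask. The recruitment ceiling is higher only because, in previous experience, "a number of 30 users was not quite achieved when taking into account drop outs and no shows". Section 8.12 gives the ceiling: "Up to 45 nasal and nasal pillows mask users for OSA therapy will be recruited into this trial".

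The synopsis (6.1) says: "An important factor in this investigation will be the testing of all four seal sizes (small, medium, large and wide". The readable text gives no number of wearers per seal.

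On home use, the text speaks of one mask per participant. The schedule in 8.10 lists "Issue complete Nasal mask with UI" at Visit 2. Section 6.1 says "The mask and CPAP (if from the research pool) will be returned to the Institution" at the end. Section 9.10 analyses those who consent and are "fitted with a mask that they attempt to sleep on will be included in the analysis". Sections 8.4.2 and 8.5 treat seal size as something to be determined for each participant with a sizing tool. No readable section describes wearing several seals in turn at home.

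Section 7.3 gives a different population: up to 15 participants, from a different recruitment source.

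**The concern.** A detection figure for 30 users applies to problems that all 30 can meet. A problem that arises at home with one seal only, such as a leak or pressure point peculiar to the wide seal, can be met only by the people wearing that seal. The number that counts for it is that seal's wearers, not the total enrolled.

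As worded, 9.6 covers all problems, so a reader could take 97% or 99% as assurance for each of the four seals the study sets out to test. Comfort, acceptance and adequate treatment in home use are primary outcomes (8.4.1), and leak is a listed variable (8.5). Section 11 says that the study is intended for internal product development, but it also allows the results to be used in marketing or regulatory documents. A clean result for a seal worn by only a few people could then be read as stronger evidence than it is.

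**Working it through.** **Inputs.** 30 users, minimum 97% and average 99% (9.6); ceiling of 45 (6.1, 8.12, 9.6); four seals (6.1). Assumption: one seal per participant at home.

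**The plan's own figure.** The 97% and 99% are cited from guidance. The documents give no per-user probability p of meeting a problem, so the figures cannot be reproduced from them.

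**Step 1: wearers per seal, for any split.**
- Two seals with 30 wearers each need 2 × 30 = 60 participants, more than 45. At most one seal can reach 30, so at least three cannot.
- The least-worn seal has at most floor(45/4) = 11 wearers. With 30 evaluable participants it has at most floor(30/4) = 7.
- For all four seals to have 30 wearers among 45 participants, each participant would have to use on average 4 × 30/45 = 2.67 seals at home.

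This step needs no assumption about p or about how participants divide between seals.

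**Step 2: what zero occurrences would show.** If none of n wearers has a given problem, the exact two-sided 95% upper limit on its frequency is 1 − 0.025^(1/n).

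| Wearers n | Upper limit |
|---|---|
| 30 | 0.116 (12%) |
| 11 | 0.285 (28%) |
| 7 | 0.410 (41%) |

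This step also needs no assumed p.

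**Step 3: range for the share of seal-specific problems found.** Suppose the average share found would be 99% with 30 wearers of the seal, and let p vary between problems. The share missed with n wearers is the average of (1−p)^n over problems.
- *Lower end.* Given E[(1−p)^30] = 0.01, Jensen's inequality gives E[(1−p)^n] ≤ 0.01^(n/30). The share found is therefore at least 1 − 0.01^(7/30) = 0.659 at 7 wearers and at least 1 − 0.01^(11/30) = 0.815 at 11. These values are reached when every problem has the same p = 1 − 0.01^(1/30) = 0.142.
- *Upper end.* Fewer wearers cannot find more on average, so the share is at most 99%. It is reached in the extreme case where 99% of problems affect every wearer and 1% affect none.
- *A case between, with assumed values.* Let 95% of problems have p = 0.50 and 5% have p = 0.052. The share found is 99.0% at 30 wearers, 97.2% at 11 and 95.8% at 7.

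The same 99% average at 30 users is thus compatible with about 66% to 99% at 7 wearers and about 82% to 99% at 11. The 97% is stated as a minimum, not an average, so it is not used here.

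**Step 4: the other population figure.** With the 15 participants of section 7.3, no seal could reach 30.

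**The case against.** The strongest reply is that 9.6 calls 30 users sufficient, not necessary. Fewer than 30 wearers removes the stated assurance but does not show a lower yield. That stands. A reader might infer that seal-specific problems will be missed, or that detection falls to 66% or 82%. The documents do not support this: p is not stated, and those values are only the lower ends of ranges that reach 99%.

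A reader might also infer that the figure applies to no single seal. That goes too far, because one seal could have 30 wearers and the figure could then apply to it.

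One seal per participant is an assumption. Text is redacted in 6.1 just after the Visit 2 description. Section 8.6 shows only a figure caption, figures in 8.10 are not shown, and the Sizing Guide and questionnaires are not visible. A rule on seal allocation or on reporting by seal could be there. This limits confidence, although 6.1, 8.4.2, 8.5, 8.10 and 9.10 all fit one seal per person. Trying several seals at the fitting would not change the point, which concerns home use.

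Finally, the plan promises no detection by seal, its objectives (7.2) concern the mask as a whole, the study is mainly for internal development, and 9.5 says no statistical design is required. That is fair, and it is why no larger sample is asked for. It does not settle the matter, because 9.6 itself makes an unlimited quantitative claim while 6.1 singles out the four seals.

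**Conclusion.** The point holds as a limit on what 9.6 can claim. With one seal per participant at home, at least three of the four seals must have fewer than 30 wearers, and the least-worn has at most 11 of 45 or 7 of 30. For home-use problems confined to such a seal, the 30-user figure gives no assurance. For the least-worn seal, zero occurrences of a problem could not exclude a frequency of 28% with 11 wearers or 41% with 7, against 12% with 30.

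The count rests only on the one-seal assumption and the ceiling of 45. Any detection percentage for a seal also depends on the unstated p. The 30-user figure is not disputed for problems that every user can meet, and nothing here shows that the study is too small for its general usability aim. Confidence is moderate because relevant text is not visible.

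**What to change.** In 9.6, limit the 97% and 99% statement to problems that all users can meet. Add that it gives no assurance for problems confined to a seal worn by fewer than 30 participants.

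In the study report, give for each seal size the number of wearers, the problems found, comfort and leak, with exact 95% limits for proportions.

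Reconcile the population in 7.3 (up to 15) with the 45 in 6.1, 8.12 and 9.6.

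The cost is a less favourable stated figure and a little more reporting. Limiting the claim and reporting by seal need no extra participants and no change to recruitment or conduct.

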9.7. Pass/Fail Criteria

9.8. Statistical Termination

No interim analysis will be conducted as statistical outcomes will not change the conduct of the study.

9.9. Statistical Procedure Deviations

Statistical procedure deviations will be reported to the principal investigator and the sponsor. Deviations from the original statistical plan will be explained in the final study report.

9.10. Selection Criteria

All participants who consent, and are fitted with a mask that they attempt to sleep on will be included in the analysis. Please see section 8.10 for information on participant flow throughout the trial.

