7.1. Hypothesis

7.2. Objectives

Primary Objective:

- To evaluate the performance, comfort and ease of use of the F&P Nasal mask in a home environment in regards to the participants' view on overall comfort, overall experience and satisfaction.
- To gain usability insights into mask fitting and removal from all participants enrolled in this mask study.

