8.4.2. Secondary Outcomes

- Seal size determination using the sizing tool
- To obtain 3D face scanning and head measurements to assist with future product development (CIA-107)

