8.9. Point of Enrolment

[figure not shown]
Participants will be recruited from patients who are prescribed either APAP, CPAP or Bi-level PAP for OSA at Clinical Trials of Florida. The principal investigator (or those identified in delegation log) will ask the subjects whether they're interested to take part in the trial. The patients who provide informed consent and meet the inclusion/exclusion criteria will then be enrolled into the trial.

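### If section 9.10's analysis set is applied to the Visit 2 outcomes, it leaves out fitting, sizing and static-leak data from participants who never tried to sleep in the mask

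*Combined protocol and SAP*

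**What the plan says.** Section 9.10 (Selection Criteria) states the analysis population: "All participants who consent, and are fitted with a mask that they attempt to sleep on will be included in the analysis". It then refers to section 8.10 for participant flow. No other analysis set appears in the readable text, and 9.10 does not distinguish between outcomes.

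Other sections bear on who should count for the fitting outcomes:

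- Section 7.2 lists as a primary objective: "To gain usability insights into mask fitting and removal from all participants enrolled in this mask study".
- Section 8.9 places enrolment before any fitting: "The patients who provide informed consent and meet the inclusion/exclusion criteria will then be enrolled into the trial".
- The event table in section 8.10 puts "Mask fitting with F&P Nasal mask" and "Static Leak Measurement" at Visit 2, with a participant and a researcher questionnaire. The in-home trial also starts at Visit 2 and is listed after these rows.
- Section 6.1 has first impressions recorded at the fitting visit and calls the testing of all four seal sizes an important factor.
- Section 8.4.2 names a secondary outcome that needs no sleep: "Seal size determination using the sizing tool".
- Section 9.6 bases the sample size on finding usability problems with 30 users. It sets recruitment at up to 45 because drop-outs and no-shows had kept numbers short of 30 before.

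**The concern.** The 9.10 rule has a condition, the attempt to sleep, that comes after the Visit 2 data have been collected. For outcomes completed at Visit 2 this selects participants on something that happens later and may depend on the outcome itself. Someone who cannot be fitted, who refuses the mask after trying it, or who takes it home and never wears it may do so because the fit, the seal size or the leak was poor.

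If such people are left out, two things follow. Fitting and sizing summaries describe only users for whom the fitting went well enough to continue. And a problem bad enough to stop someone before the first night is seen at the visit but has no place in the analysed results, although finding such problems is the stated basis of the sample size. Section 11 allows the results to be used in marketing or regulatory documents, so the denominator matters beyond internal development.

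**Working it through.** **1. The plan's own figure.** Section 9.6 says 30 users find at least 97% of problems, and 99% on average. The usual discovery formula is 1 − (1 − p)^n, where p is the chance that one user shows a given problem. The documents give no p, so the claim cannot be reproduced. Solving at n = 30:

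- 97%: p = 1 − 0.03^(1/30) = 0.110
- 99%: p = 1 − 0.01^(1/30) = 0.142

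Going from 30 to 45 leaves room for a loss of 1 − 30/45 = 33.3%. Section 9.6 does not divide that loss between people who never attend and people who are fitted but never use the mask. The present point does not depend on these figures.

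**2. Who falls between the rules.**

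| Participant | Enrolled (8.9) | Visit 2 fitting data | Meets 9.10 |
|---|---|---|---|
| Never attends Visit 2 | Yes | None | No |
| Fitting attempted, not fitted or mask refused | Yes | Yes, at least in part | No |
| Fitted, never tries to sleep in the mask | Yes | Yes | No |
| Fitted, tries to sleep at least once | Yes | Yes | Yes |

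The middle two rows hold the recoverable data. Sizing and removal have no row of their own in the event table; I take sizing as part of the fitting, and removal as covered where it is observed at Visit 2.

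**3. How many records.** Let N be the number with a fitting attempted and k the number in the middle two rows. The share left out is k/N. The documents give no k, so 1 to 5 is an assumption. N = 30 and N = 45 are the target and ceiling in 9.6.

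- N = 30: 1/30 = 3.3% to 5/30 = 16.7%
- N = 45: 1/45 = 2.2% to 5/45 = 11.1%
- k = 0: no effect

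**4. What this does to finding problems.** Suppose a problem affects a share p of users, and a fraction f of those affected stop before the first night. Assuming users are independent, the chance that the 9.10 set contains at least one affected user is 1 − [1 − p(1 − f)]^N. Both p and f are assumed; take p = 0.10.

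| f | p(1 − f) | N = 30 | N = 45 |
|---|---|---|---|
| 0 | 0.10 | 95.8% | 99.1% |
| 0.5 | 0.05 | 78.5% | 90.1% |
| 1 | 0 | 0% | 0% |

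The f = 0 row is also the chance in the fitting-attempted set, whatever f is. The loss is therefore nil for problems that stop nobody and complete for problems that always stop the user. No number of recruits repairs the last row under the 9.10 rule.

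**The case against.** The strongest reply is that 9.10 says who is included and does not say that nobody else is, or that it covers every outcome. A reader might infer that the plan discards Visit 2 data from everyone else; the text does not say so. Section 7.2 speaks of insights, section 9.5 says no statistical design is needed, and the interview record could meet that objective whatever 9.10 does to the summaries. This stands, and it is why the point is conditional. Even so, a rule under this heading, with no other set visible, will naturally be read as the population for all summaries, and descriptive results still need a denominator.

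A second reply is that the readable text is incomplete. Sections 7.4 and 9.7 and the figures in 8.10 cannot be read, the readable statistical text begins at 9.5, and the questionnaires in Appendices B and C are not shown. An outcome-specific rule may exist there. This also stands.

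Third, the group may be small. One attempt to sleep is enough for inclusion, participants already use nasal or nasal pillows masks, and patients intolerant to PAP are excluded. Section 9.6 attributes past shortfalls to drop-outs and no-shows, not to failed fittings. Milder forms of the same problem may still appear among those who continue. All of this limits the likely size but does not remove the mismatch.

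A reader might also infer that acceptability is overstated. The documents do not support that: section 8.4.1 ties acceptance to in-home use, so the 9.10 set is a defensible choice for it, and any figure would rest wholly on assumed response rates. Nor can 7.2 be met literally for everyone enrolled, because those who never attend Visit 2 have no fitting data.

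**Conclusion.** The point holds in conditional form. As the only readable analysis-set rule, 9.10 is narrower than the fitting and removal objective in 7.2 and asks for a night's attempt that the Visit 2 outcomes do not need. Applied to those outcomes, it leaves out the users whose fitting problem stopped them before the first night.

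The direction depends on why people are left out. Mask-related reasons make fitting and sizing results look better than they are; unrelated reasons, such as illness after a good fitting, can act either way. The size cannot be stated. The shares and discovery chances above show what is possible under assumed counts and rates and are not estimates for this trial. The conclusion rests on no contrary rule existing in the unreadable parts. For in-home comfort, leak, PAP data and acceptability, the 9.10 set is reasonable and needs no change.

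**What to change.** Amend section 9.10 as follows:

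- Fitting results, removal observed at Visit 2, seal sizing and static leak (where measured) use every consented, eligible participant for whom a fitting was attempted at Visit 2.
- The current 9.10 set is kept for in-home comfort, leak, PAP data and acceptability.
- The report gives the number, with reasons where given, of participants enrolled but not fitted and of participants fitted who never tried to sleep in the mask.

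If a rule to this effect already exists elsewhere in the plan, a cross-reference in 9.10 is enough.

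No new visit, measurement or sample size is needed: the Visit 2 data are already scheduled in 8.10, and section 8.11 already has discontinuation reasons entered on the CRF. The costs are slightly more reporting and possibly less favourable figures. Some reasons will be missing, because 8.11 does not oblige participants to state them and lets them return to their usual therapy during the study, so non-use without withdrawal may have no recorded reason.

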9.11. Statistical Data Management

Fisher and Paykel Healthcare may consult an external statistician to assist with the analysis of the data.

10. Adverse Events and Termination

An Adverse Event (AE) is any adverse change from the participant's baseline condition, i.e., any unfavourable and unintended sign or symptom or disease that occurs during the course of the study, whether or not considered related to the PAP treatment. All clinically significant AEs occurring during the study that were not present prior to the commencement of PAP treatment, will be recorded in the CRF and source document and followed by the Investigator until resolution or stabilization occurs in accordance with GCP.

Serious AE's are considered to be AE's that result in any of the following outcomes, regardless of their relationship to the PAP treatment:

- Death
- A life-threatening AE
- In-patient hospitalization or prolongation of existing hospitalization
- A persistent or significant disability/incapacity
- A congenital abnormality/birth defect

Name: [name]

Address: [name]

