6.2. Literature Review

Obstructive Sleep Apnea (OSA) is a common sleep breathing disorder affecting up to 9% of the adult population¹ and is characterized by periodic collapse of the upper airway during sleep. The standard treatment for obstructive sleep apnea is PAP, which consists of pressurized air applied to the nose via an interface. PAP includes continuous positive airway pressure (CPAP), automatic positive airway pressure (APAP) and Bilevel positive airway pressure (Bilevel PAP). Despite the effectiveness of PAP in abolishing upper airway obstruction, acceptance of and adherence with therapy has been sub-optimal^{2,3}. Reasons for the low compliance include nocturnal awakenings, incorrect therapeutic pressure and primarily discomfort due to poor mask fit. Poor mask fit can result in facial abrasion, leak causing fluctuations in therapeutic pressure and irritation of the eyes^{4,5}.

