8.8. Inclusion / Exclusion criteria

Inclusion Criteria

- AHI ≥ 5 from the diagnostic night
- ≥ 18 years of age
- Either prescribed APAP, CPAP or Bi-level PAP for OSA
- Existing nasal or nasal pillows mask users (ideally a 70%:30% split)
- Fluent in spoken and written English

Exclusion Criteria

- Inability to give informed consent
- Patient intolerant to PAP
- Anatomical or physiological conditions making PAP therapy inappropriate
- Current diagnosis of respiratory disease or CO₂ retention
- Pregnant or think they may be pregnant

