10.3. Reporting Adverse Events

Any serious AE, due to any cause, that occurs during the study period, must be reported immediately (within the next business day) by telephone to the sponsor. In addition to the initial telephone report, a Serious Adverse Event form must be completed and sent via facsimile to the sponsor. All serious AE's must also be recorded on the AE page of the CRF. Additionally, all serious AE's must be reported to the Independent Review Board (IRB) as per the IRB's requirements.

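### Section 10 defines an AE as a change from baseline but records only what was absent before PAP began, so some non-serious worsening can go unrecorded

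*Combined protocol and SAP*

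**What the plan says.** The opening paragraph of section 10 contains two adjacent statements.

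- The definition: an AE is "any adverse change from the participant's baseline condition". The text then explains this as any unfavourable, unintended sign, symptom or disease arising in the course of the study, related to PAP or not.
- The recording rule: "All clinically significant AEs occurring during the study that were not present prior to the commencement of PAP treatment, will be recorded". The same sentence requires these events to be "followed by the Investigator until resolution or stabilization occurs in accordance with GCP".

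Serious AEs have their own rule in 10.3, with no such limit: "All serious AE's must also be recorded on the AE page of the CRF".

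On the population, 6.1 states: "Up to 45 OSA participants who currently use a nasal or nasal pillows CPAP mask will be recruited". The inclusion criteria in 8.8 agree: "Existing nasal or nasal pillows mask users (ideally a 70%:30% split". Section 8.10 puts consent at Visit 1 and the start of the in-home trial of the F&P Nasal mask at Visit 2.

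**The concern.** The definition looks back to the participant's baseline condition. The recording rule looks back to the start of PAP. In a study of people starting PAP for the first time, the two would nearly coincide. Here they do not, because every participant was on PAP before consent.

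The recording rule also turns on whether something was present before, and does not say what to do when something present before gets worse. For a new mask given to established users, getting worse is a natural form of harm.

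What is at stake is consistent capture of non-serious events. Two members of site staff could treat the same worsening differently. An event left out under this sentence also falls outside its follow-up requirement. Section 5.2 describes the expected risk as slight discomfort, so the harms the sponsor expects are mostly of the non-serious kind that 10.3 does not pick up.

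**Working it through.** The point rests on no figure in the plan, so there is nothing to recompute. The check is to set the passages side by side.

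**Step 1: when did PAP begin?** By 6.1 and 8.8, participants are existing mask users prescribed PAP. Read literally, PAP therefore began before Visit 1, at a different time for each person. Study baseline comes later, and the trial mask later still (Visit 2, 8.10).

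**Step 2: what does PAP treatment mean?** Section 6.2 uses PAP for the therapy: "The standard treatment for obstructive sleep apnea is PAP". Section 5.2 treats the mask as the means of delivering it, and 6.5 keeps participants on their prescribed pressure throughout. The literal reading is therefore the natural one. Against that, 8.1 calls the trial mask the intended treatment, and section 10 speaks of relatedness to the PAP treatment where a device study would usually mean the device under test. A site could take the phrase to mean the trial mask, but this is the weaker reading.

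**Step 3: does the rule reach worsening?** A strict reader asks whether the condition was there before. If it was, its worsening is not recorded. A lenient reader treats the worsening itself as the AE, which was not there before, and records it. The sentence does not choose between them.

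**Step 4: apply this to clinically significant events after the trial mask is fitted.** All four meet the definition.

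| Event | Recorded, literal reading | Recorded, trial-mask reading |
|---|---|---|
| Non-serious, wholly new | Yes | Yes |
| Non-serious worsening of a condition older than PAP | Strict: no. Lenient: yes | Strict: no. Lenient: yes |
| Non-serious worsening of a complaint that began on the usual mask | Yes, because it began after PAP did | Strict: no. Lenient: yes |
| Serious | Yes, by 10.3 | Yes, by 10.3 |

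Under the natural reading, the gap is the second row only. The less natural reading adds the third.

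**Step 5: is there another rule for non-serious AEs?** None appears in the available text. Section 8.11 records the reason for discontinuation, but only for those who discontinue. The questionnaires and sleep diary may reveal problems, but they are not AE records.

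**The case against.** The best defence is that the rule governs AEs, and an AE has just been defined as an adverse change. Worsening is an adverse change, and that change did not exist before PAP, so it is recorded. This is a fair reading and may be the one intended. It does not close the point. The definition also speaks of a sign, symptom or disease, which invites the question of whether that symptom was already there. The change-based reading also leaves the filter with almost nothing to do. What stands is that omission is permitted, not required.

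A second defence is that the answer may lie in text not available here. The end of 5.2 on AE reporting is redacted, and 10.1 to 10.2, the case report form (CRF) and the appendices cannot be seen. This stands as a limit on the point.

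Two stronger readings are tempting, and the documents do not support them.

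- A reader might infer that the facial abrasion and eye irritation named in 6.2 would be missed. Where such complaints come from mask fit, they began after PAP did, so the literal rule records them. They fall into the gap only under the trial-mask reading.
- A reader might infer that baseline itself is undefined, so that an event between Visits 1 and 2 might not count as an AE. Section 6.1 says "This study will involve a baseline visit (Visit 1"). The references to baseline in 6.5, 8.2 and 8.10 concern PAP device data, not the participant's condition. The definition in any case extends to whatever occurs during the study, which includes the interval between those visits.

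**Conclusion.** The mismatch is real and minor. The recording rule is narrower than the definition it follows, and its reference point does not suit a population already on PAP. The consequence is limited to non-serious, clinically significant worsening of conditions older than PAP, left out by a strict reader. It extends to complaints from the usual mask only if PAP treatment is taken to mean the trial mask.

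No number of missed events can be given, because the documents contain no AE rates. No study result turns on the point: AEs are not among the outcomes in 8.4, comfort is collected separately by questionnaire, and 9.5 states that no statistical design is required. Section 11 describes the study as mainly for internal development, and the regulatory use it names concerns efficacy.

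It would be wrong to conclude that the plan excludes worsening or that safety capture as a whole is unsound. Serious AEs are fully covered by 10.3, and wholly new non-serious AEs on the trial mask are recorded under every reading. The conclusion assumes that the redacted or unavailable text does not already resolve the wording.

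**What to change.** Bring the two sentences in section 10 to one reference point. For example: *Clinically significant AEs will be recorded if they are new, or have become worse in severity or frequency, compared with the participant's baseline condition.* The follow-up requirement can stay attached as it is.

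If the AE page of the CRF does not already capture it, add one item stating whether onset was before or after first fitting of the F&P Nasal mask. Events could then be placed relative to the study exposure without narrowing what is recorded.

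The cost is one sentence and, at most, one CRF field. The downside is that a few more minor events will be recorded and followed. The change does not alter participants' treatment or the handling of serious AEs.
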